6.2 IRINOTECAN(CPT-11, CamptosarTM), NSC #616348

Mechanism of Action: Irinotecan is a semisynthetic water-soluble analog of camptothecin that exerts its cytotoxic effect through inhibition of the nuclear enzyme topoisomerase I. Irinotecan is a prodrug that undergoes deesterification to a much more potent topoisomerase-I inhibitor, SN-38. The lactone forms of both irinotecan and SN-38, undergo pH dependent hydrolysis to a hydroxy acid (carboxylate) species. SN-38 is glucuronidated to SN-38G.

Formulation & Stability: Each ml of irinotecan contains 20 mg irinotecan (on basis of the trihydrate salt) ; 45 mg sorbitol ; and 0.9 mg lactic acid. When necessary, pH has been adjusted to 3.5 (range, 3.0 to 3.8) with sodium hydroxide or hydrochloric acid. Irinotecan is supplied in amber, glass, single-dose vials containing 40 mg (2ml) and 100 mg (5ml) of irinotecan hydrochloride (on the basis of trihydrate salt) as a 20 mg/mL solution. The intact vials should be stored at room temperature and protected from light. It is recommended that the vial (and backing/plastic blister) should remain in the carton until the time of use.

Guidelines for Administration: Irinotecan must be diluted before infusion. Irinotecan should be diluted in 5% Dextrose Injection USP (preferred) or 0.9% Sodium Chloride Injection, USP, to a final concentration range of 0.12 to 2.8 mg/mL. The solution is physically and chemically stable for up to 24 hours at room temperature (approx 25°C) and in ambient fluorescent lighting. Solutions diluted in 5% Dextrose Injection, USP, and stored at refrigerated temperatures (approximately 2° to 8°C), and protected from light are physically and chemically stable for 48 hours. Refrigeration of admixtures using 0.9% Sodium Chloride Injection, USP, is not recommended due to a low and sporadic incidence of visible particulates. Care should be taken to avoid extravasation; the use of a central line is suggested.

Irinotecan should be administered as an intravenous infusion over 60 minutes.

Irinotecan Toxicity:

Likely (happens to 21-100 children out of 100)	Less Likely (happens to 5 -20 children out of 100)	Rare (happens to less than 5 children out of 100)

 • Diarrhea (can be immediate) • Cholinergic symptoms : rhinitis, increased salivation, miosis, lacrimation, diaphoresis, flushing. • Mucositis • Nausea and vomiting • Stomach pain • Loss of appetite • Fever • Loss of body water • Loss of strength and energy • Decrease in the number of red and white blood cells and platelets made in the bone marrow • Eosinophilia • Hair loss • Elevations in transaminases, alkaline phosphatase, bilirubin, 	
 • Mildly high liver and kidney function tests • Constipation • Delayed diarrhea • Headaches • Pain at injection site • Blood-clots** • Anemia • Thrombocytopenia • Rash • stomatitis • dyspepsia 	
 • Skin inflammation • Trembling • Blood in the urine • Mildly increased level of protein and glucose in the urine • Low amount of protein in the blood • Mouth sores • Headache • Dizziness & hypotension • Sensation of warmth on face • Inflammation of the large intestine • Ileus • Anaphylaxis, • Dehydration • Bradycardia • Disorientation/confusion, • pain at infusion site • Pneumonitis • Inflammation of the lungs with cough and congestion

**This toxicity is seen more commonly when irinotecan is given in combination with fluorouracil and leucovorin. It may rarely be a life threatening event.

Unknown Frequency and Timing: Fetal toxicities and teratogenic effects of irinotecan have been noted in animals at doses similar or less than those used in humans. Toxicities include: decreased skeletal ossification, multiple anomalies, low birth weight and increased fetal mortality. It is not known if irinotecan is excreted into breast milk but it is excreted into rat milk.

Supplier: Irinotecan is commercially available. See also package insert for further information.

6.3 TEMOZOLOMIDE(TEMODARTM) NSC#362856

Pharmacology: An orally administered alkylating agent, a second generation imadazotetrazine. A prodrug of MTIC, temozolomide spontaneously decomposes to MTIC at physiologic pH. The drug exerts its effect by cross-linking DNA. This is likely a site specific alkylation at the O6-position of guanine with some effect at the N7 position. Temozolomide reaches its peak concentration in 1 hour. Food reduces the rate and extent of absorption. It has an elimination half-life of 1.13hr (intraperitoneally) and 1.29hr (orally) with an oral bioavailability of 0.98. Total apparent body clearance is 100ml/min/m² and plasma elimination half-life is ~100 minutes.

Temozolomide Toxicity:

Likely (happens to 21-100 children out of 100)	Less Likely (happens to 5 -20 children out of 100)	Rare (happens to less than 5 children out of 100)

 • Anorexia • Constipation, • Nausea, • Vomiting, • Myelosuppression 	
 • Abdominal pain, • Diarrhea, • Headache, • Rash, itching, • Urinary frequency and/or infection • Mucositis, • Lethargy, • Peripheral edema • Alopecia • Hepatotoxicity 	
 • Convulsions, • Anaphylaxis, • Hemiparesis, • Dizziness, • Ataxia, • Confusion, • Dysphagia, • Anxiety, • Thrombo-embolism (L) • Prolonged lymphopenia with increased risk of infection or death • Amnesia, • Insomnia, • Depression, • Myalgia, • Diplopia, • Visual changes • Secondary tumors or cancer • Hepatic failure

Formulation and Stability: 5mg, 20mg, 100mg, 140mg, 180mg, and 250mg capsules, stored at room temperature.

Guidelines for Administration: See also Treatment and Dose Modifications in Section 4.0.

There is a potential for medication errors involving temozolomide capsules resulting in drug overdosages, which may have been caused by dispensing/taking the wrong number of capsules per day and/or product usage exceeding the prescribed dosing schedule.

Temozolomide capsules are available in six different strengths, each color-coded according to strength. Capsules are available in 5-count and 14-count packages, except the 250 mg capsule strength, which is only available in a 5-count package.

Capsule Strength	COLOR
5 mg	Green Cap
20 mg	Yellow Cap
100 mg	Pink Cap
140 mg	Blue Cap
180 mg	Orange Cap
250 mg	White Cap

When dispensing, it is extremely important that prescribing and dispensing include clear instructions on which capsules, and how many of each capsule(s) are to be taken per day. Only dispense what is needed for the course, and clearly indicate how many days of dosing the patient will have and how many days are without temozolomide dosing. When counseling patients, it is important for each patient / parent to understand the number of capsules per day and the number of days that they take temozolomide. It is also important for the patient/parent to understand the number of days that they will be off the medication

Each type of temozolomide capsule must be dispensed in a separate vial or in its original glass bottle. Based on the dose prescribed, determine the number of each strength of temozolomide capsules needed for the full course. For example, 275 mg/day for 5 days would be dispensed as five 250-mg capsules, five 20-mg capsules, and five 5-mg capsules. Label each container with the appropriate number of capsules to be taken each day. Dispense to the patient/parent, making

sure each container lists the strength (mg) per capsule and that he or she understands to take the appropriate number of capsules of temozolomide from each bottle or vial to equal the total daily dose prescribed by the physician.

For children unable to swallow the capsules whole, the oral capsules may be formulated into a suspension. To prepare a 10 mg/mL suspension titrate the contents of ten 100 mg capsules (1000 mg) , 500 mg povidone K-30 and 25 mg anhydrous citric acid dissolved in 1.5 mL purified water in a glass mortar to form a uniform paste. To the paste add 50 mL of Ora-Plus ® by adding a small amount, mixing and then adding the balance. Transfer to a glass graduated cylinder Add Ora-Sweet® or Ora-Sweet® SF to a total volume of 100mL by rinsing the mortar with small amounts of the syrup (Ora-Sweet® or Ora-Sweet® SF). Rinse at least four times. Package in an amber plastic prescription bottle. The packaged suspension is stable for 7 days at room temperature or 60 days in the refrigerator. The suspension should be shaken well before each use. Procedures for proper handling and disposal of cytotoxic drugs should be used when preparing the suspension. (Trissel LA, Yanping Z, Koontz SE. Temozolomide stability in extemporaneously compounded oral suspensions. *Int J Pharm Compounding* 10:396-9, 2006).

Alternatively, the capsules can be opened and mixed with apple sauce or juice.

Supplier: Commercially available. See also package insert for further information.

6.4 GRANULOCYTE COLONY STIMULATING FACTOR(G-CSF) (Neulasta,Pegylated filgrastim Or Neupogen, Filgrastim).

6.4.1 NEULASTA (PEGFILGRASTIM):

Source and Pharmacology:

Pegfilgrastim is the pegylated form of recombinant methionyl human G-CSF (filgrastim). Pegfilgrastim is produced by covalently binding a 20-kilodalton (kD) monomethoxypolyethylene glycol molecule to the N-terminal methionyl residue of filgrastim. The molecular weight of pegfilgrastim is 39 kD. G-CSF is a lineage specific colony-stimulating factor which regulates the production of neutrophils within the bone marrow and affects neutrophil progenitor proliferation, differentiation, and selected end-cell functional activation (including enhanced phagocytic ability, priming of the cellular metabolism associated with respiratory burst, antibody dependent killing, and the increased expression of some functions associated with cell surface antigens). After subcutaneous injection the elimination half-life of pegfilgrastim ranges from 15 to 80 hours and the time to peak concentration ranges from 24 to 72 hours. Serum levels are sustained in most patients during the neutropenic period postchemotherapy, and begin to decline after the start of neutrophil recovery, consistent with neutrophil-dependent elimination. After subcutaneous administration at 100 mcg/kg in 37 pediatric patients with sarcoma, the terminal elimination half-life was 30.1 (+/- 38.2) hours in patients 0 to 5 years-old, 20.2 (+/- 11.3) hours in patients 6 to 11 years-old, and 21.2 (+/- 16) hours in children 12 to 21 years-old.

Neulasta Toxicity:

Likely (happens to 21-100 children out every 100 children)	Less Likely (happens to 5-20 children out every 100 children)	Rare (happens to < 5 children out every 100 children)

 Mild to moderate medullary bone pain 	
 Local pain or irritation at injection site Headache Increased alkaline phosphatase, lactate dehydrogenase and uric acid. Thrombocytopenia 	
 Low grade fever, Allergic reactions (anaphylaxis, angioedema, or urticaria), Generalized erythema and flushing, Splenomegaly, splenic rupture, sickle cell crises in patients with sickle cell disease (SCD), Excessive leukocytosis, Sweet's syndrome (acute febrile neutrophilic dermatosis) Adult respiratory distress syndrome

Unknown frequency and timing: Fetal toxicities and teratogenic effects of pegfilgrastim in humans are unknown. Conflicting data exist in animal studies. It is unknown whether the drug is excreted in breast milk.

Supplier: Commercially available. See package insert for further information.

Formulation and Stability:

Supplied as a preservative-free solution containing 6 mg (0.6 mL) of pegfilgrastim (10 mg/mL) in a single-dose syringe with 27 g, ½ inch needle with an UltraSafe® Needle Guard. The needle cover of the prefilled syringe contains drug natural rubber (a derivative of latex). Store refrigerated at 2°-8°C (36°-46°F) and in the carton to protect from light. Prior to injection, pegfilgrastim may be allowed to reach room temperature protected from light for a maximum of 48 hours. Avoid freezing.

Guidelines for Administration: See Treatment and Dose Modifications sections of the protocol

6.4.2 NEUPOGEN (FILGRASTIM):

Source and Pharmacology: Filgrastim is a human granulocyte colony-stimulating factor (G-CSF), produced by recombinant DNA technology. Filgrastim is a 175 amino acid protein with a molecular weight of 18,800 daltons manufactured by recombinant DNA technology utilizing E.coli bacteria into which has been inserted the human granulocyte colony stimulating factor gene. It differs from the natural specific colony-stimulating factor which regulates the production of neutrophils within the bone marrow and affects neutrophil progenitor proliferation, differentiation, and selected end-cell functional activation (including enhanced phagocytic ability, priming of the cellular metabolism associated with respiratory burst, antibody dependent killing, and the increased expression of some functions associated with cell surface antigens). The elimination half-life is similar for subcutaneous and intravenous administration, approximately 3.5 hours. The time to peak concentration when administered subcutaneously is 2 to 8 hours.

Formulation and Stability:

Supplied as a clear solution in 300 ug/ml ($1 \pm 0.6 \times 108$ U/mg) (1 ml or 1.6 ml) vials. Vials are preservative free and are intended to be single-use vials; do not reuse opened vials. Filgrastim must be stored between 2° and 8°C. Stability has been demonstrated for at least 24 months

when stored under these conditions. Do not use if discolored or if there is particulate matter. For IV use, dilute in D5W to concentrations > 15 ug/ml; G-CSF is incompatible with normal saline. At dilutions from 5 ug/ml to 14 ug/ml, add human serum albumin to a final albumin concentration of 2 mg/ml to protect against absorption of the GCSF to container walls (glass or plastic). Filgrastim, when diluted as described above, is compatible with a number of plastics commonly used in the manufacture of syringes, IV bags, infusion sets, and IV pump cassettes. These include polyvinyl chloride, polyolefin, and polypropylene. Diluted filgrastim should be stored at 2° to 8° C and used within 24 hours. **Do not shake or freeze.**

Guidelines for Administration:

Administer once daily, subcutaneously without dilution or if necessary dilute with 5% dextrose in water, preferably to concentrations of 15 ug/ml or greater for IV administration. Dilutions should be prepared as close to the time of administration as possible (up to 24 hours), since the product is preservative-free. When diluting Filgrastim to 5-14 ug/ml in D5W, it is necessary at all times to add human serum albumin, to reach a final albumin concentration of 2 mg/ml.

Neupogen Toxicity:

Likely (happens to 21-100 children out every 100 children)	Less Likely (happens to 5-20 children out every 100 children)	Rare (happens to < 5 children out every 100 children)

 Mild to moderate medullary bone pain 	
 Local pain or irritation at injection site Increased alkaline phosphatase, LDH and uric acid Thrombocytopenia Fever 	
 Allergic reactions (more common with IV than subcutaneous administration) Skin rash, urticaria and/or facial edema Respiratory wheezing and/or dyspnea Hypotension and/or tachycardia Low grade fever Splenomegaly Splenic rupture Worsening of existing skin rashes Sickle cell crises in patients with Sickle cell disease Excessive leukocytosis Cutaneous vasculitis Adult respiratory distress syndrome MDS or AML (in patients with severe chronic neutropenia and long term administration)

Supplier: Commercially available. See package insert for further information.

6.5 CEFIXIME (Suprax)

Source and Pharmacology: Cefixime is a third generation cephalosporin antibiotic for oral administration that inhibits bacterial cell wall synthesis by binding to one or more of the penicillin-binding proteins and interfering with the final transpeptidation step of peptidoglycan synthesis. Its spectrum of activity is similar to other third-generation agents, including Enterobacteriaceae, and β -lactamase producing *H. influenzae* and *N. gonorrhoea*, and *Staph. aureus*. It is excreted primarily by the kidney. It has a serum half-life of approximately 3-4 hours.

Formulation: Cefixime is available in a powder for oral suspension, which when reconstituted, provides 100mg/5ml. The powder for oral suspension is strawberry flavored and contains sodium benzoate, sucrose, and xanthan gum. Cefixime is available as 50ml, 75ml & 100ml bottle with powder for reconstitution.

Toxicity:

Likely (happens to 21-100 children out of 100)	Less Likely (happens to 5 -20 children out of 100)	Rare (happens to less than 5 children out of 100)
	
• Diarrhea• Abdominal pain• Nausea and vomiting,• Dyspepsia	
• Headache• Dizziness• Seizures• Anaphylaxis• Hypersensitivity reactions• Thrombocytopenia,• Leucopenia,• Neutropenia,• Eosinophilia,• Pseudomembranous colitis,• Increase in BUN/SCr and ALKP,• Hepatitis, jaundice• Stevens Johnson, 
TOXIC EPIDERMAL NECROLYSIS

Supplier: Commercially available. See package insert for further information.

6.6 CEFPODOXIMEPROXETIL (Vantin-R)

Source and Pharmacology: Cefpodoxime proxetil is a third generation cephalosporin antibiotic for oral administration that inhibits bacterial cell wall synthesis by binding to one or more of the penicillin-binding proteins and interfering with the final transpeptidation step of peptidoglycan synthesis. Its spectrum of activity is similar to other third-generation agents, including Enterobacteriaceae, and β -lactamase producing *H. influenzae* and *N. gonorrhoea*, and *Staph. aureus*. It is excreted primarily by the kidney. It has a serum half-life of approximately 2-4 hours.

Formulation: Cefpodoxime proxetil is available as 100mg & 200mg oblong tablets & powder for oral suspension, which when reconstituted, provides either 50mg/5ml OR 100mg/5ml. The powder for oral suspension is lemon cream flavored. Cefpodoxime is available as 50ml, 75ml & 100ml bottle with powder for reconstitution.

Cefpodoxime Proxetil Toxicity:

Likely (happens to 21-100 children out of 100)	Less Likely (happens to 5 -20 children out of 100)	Rare (happens to less than 5 children out of 100)
	
• Diarrhea• Diaper Rash	
• Abdominal pain• Nausea and vomiting,• Headache• Seizures• Anaphylaxis• Chest pain• Hypersensitivity reactions• Thrombocytopenia,• Leucopenia,• Neutropenia,• Eosinophilia,• Pseudomembranous colitis,• Increase in BUN/SCr and ALK Phos• Prolonged PT / PTT• Vaginal candidiasis• Aplastic Anemia• Stevens Johnson / Toxic Epidermal Necrolysis

Supplier: Commercially available. See package insert for further information.

6.7 Drug Inventory Records

The investigator, or a responsible party designated by the investigator, must maintain a careful record of the inventory and disposition of all investigational drugs.

7.0 REQUIRED OBSERVATIONS/MATERIAL AND DATA TO BE ACCESSIONED

7.1 Clinical and Laboratory Studies

All blood and urine studies must be performed within 2 weeks prior to study enrollment. Tumor disease evaluation (including appropriate imaging studies, bilateral bone marrow aspirate and biopsy for standard histology and urine catecholamines) are required within 4 weeks prior to study entry and subsequent to any prior therapy. Patients with marrow disease documented at study entry by morphology are REQUIRED to have repeat bone marrow evaluations at each subsequent disease evaluation. Initiation of protocol therapy is required within 1 week of study enrollment.

OBTAIN OTHER STUDIES AS NEEDED FOR GOOD PATIENT CARE.

Observation	Before Entry	Cycle 1	Cycles 2-34	End of Therapy
Physical Exam ⁴ (Ht, Wt, BSA, VS) Performance status ⁴ required only at entry	X	Weekly	Start of each cycle ⁸	X
CBC, Diff, Platelets ⁴	X	Twice weekly ¹	Weekly ^{1, 8}	X
AST ⁴ , ALT ⁴ , Total ⁴ + Direct Bilirubin, Albumin, Electrolytes, Calcium, Magnesium, Phosphorus, BUN, Serum Creatinine ⁴	X	Weekly	Start of each cycle ⁸	X
Plasma lactate and calculated anion gap (only for patients in the oral solution cohort)	X	Day Four ⁹		
Serum β -HCG ^{2,4}	X			
Urine catecholamines VMA/HVA	X		X ⁷	X ⁷
Bilateral BM Aspirate + Biopsy for morphology ^{4, 5, 10}	• X ¹⁰		X ^{5, 7, 10}	X ^{7, 10}
Tumor anatomic imaging (CT or MRI scan) ^{3, 4}	X		X ⁷	X ⁷
MIBG diagnostic scan ^{4, 6} Use same isotope with each scan	X		X ⁷	X ⁷
Patient diary		X	X	
Plasma pharmacokinetic samples (required for patients in oral solution cohort; optional for patients in the phase 2 portion)		See Section 8		
Blood for UGT1A1 and AURKA genotyping (optional)		See Section 8		
Archival tumor tissue submission (if consent)		See Section 8		

1. More frequent CBCs may be needed as part of good patient care.
2. Obtain for females 10 years of age and older or post-pubertal.
3. Tumor imaging = CT and/or MRI for optimum visualization of all areas of bulk tumor (primary & metastasis). All disease status tests must be performed \leq 4 weeks prior to study entry and subsequent to any intervening therapy.
4. Required for verification of eligibility. All results should be faxed to NANT Operations Center with study registration eligibility. An eligibility worksheet is available in the data forms packet on NANT website (www.nant.org).
5. Patients with bone marrow disease present at study entry should have a diagnostic bone marrow sent with each disease evaluation. All disease status tests must be performed \leq 4 weeks prior to study entry and subsequent to any intervening therapy. To confirm a bone marrow response of CR, an additional bone marrow examination for morphology (for a total of 2 bone marrow exams) must be done a minimum of three weeks apart (section 11.2.1).
6. ¹²³I-MIBG scans are preferred. Omit for patients known to be MIBG non-avid and replace with ¹⁸FDG-PET (preferred) or bone scan. All disease status tests must be performed \leq 4 weeks prior to study entry and subsequent to any intervening therapy.
7. Perform disease re-staging after day 14 of cycles 2, 4, 8, and then every 4 cycles thereafter.
8. All observations timed for the start of a cycle are to be obtained prior to the start of Day 1 therapy (and do not necessarily need to be obtained prior to resuming oral cephalosporin on Day -1; if studies obtained between Day -2 and Day 0 and meet criteria to proceed with subsequent cycle, do not need to be repeated on Day 1).
9. If plasma lactate elevated above baseline draw on Day Four draw, obtain a venous blood gas to determine if pH < 7.3 (= grade 3 acidosis in CTCAE version 4 and therefore a potential dose-limiting toxicity).
10. If patient is co-enrolled on NANT 2004-05, please also submit specimens for biology study for these timepoints.

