3.0 PATIENT ELIGIBILITY CRITERIA AND REGISTRATION

3.1 Patient Preparation for Study Entry and Registration

Patient Registration On Study:

Eligible patients will be registered by contacting the NANT Operations Center at Children's Hospital Los Angeles Monday through Friday, 8:30am – 5:00 pm Pacific Time at [contact] except holidays. The information requested on the N2009-03 Demographic, Eligibility, and On Study Forms must be completed, and the signed informed consent along with the documentation confirming eligibility must be FAX'd to [contact] for registration to occur. Each patient will be assigned a unique NANT registration and study subject number. The dose level will be assigned by the NANT Operations Center at the time of study registration. Once eligibility is verified, the NANT Operations center will send an email confirming registration which must be received prior to starting any protocol therapy or the patient will be declared ineligible. This email will also assign the dose level, and will be sent to the treating facility, Study Chair, and Study Vice-Chair. A registration worksheet is available on the web site (www.NANT.org) in the data forms packet to assist institutions with registration requirements for this protocol.

Contact Person: Research Coordinator
NANT Operations Center
Children's Hospital Los Angeles
[name]
Los Angeles, CA 90027
[contact]
[contact]

To allow non-English speaking patients to participate in this study, bilingual health services will be provided in the appropriate language when feasible.

Patients are required to start protocol therapy within 1 week of study enrollment. The start of protocol therapy is defined as the start of oral cephalosporin in Day -1. Protocol therapy must not start until the patient has been enrolled.

Co-enrollment on NANT 2004-05 (Neuroblastoma Biology Study) is strongly encouraged.

Important note: The eligibility criteria listed below are interpreted literally and cannot be waived.

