3.2.10 Organ Function Requirements

3.2.10.1 Hematologic Function:

Patients must meet the following hematologic criteria for enrollment onto the oral solution cohort of the study regardless of bone marrow disease status:

- a. ANC: $\geq 1000/\mu\text{L}$ (no hematopoietic growth factors within 7 days of the start date of protocol therapy); and
- b. Platelet count: $\geq 100,000/\mu\text{l}$, transfusion independent (no platelet transfusions within 1 week of the start date of protocol therapy).

Patients with bone marrow disease who meet the above count criteria will be eligible to enroll in the oral solution cohort of the study and will be evaluable for hematologic toxicity.

Patients must meet the following hematologic criteria for enrollment onto the phase 2 portion of the study unless they have bone marrow disease:

- a. ANC: $\geq 1000/\mu\text{L}$ (no hematopoietic growth factors within 7 days of the start date of protocol therapy); and
- b. Platelet count: $\geq 100,000/\mu\text{l}$, transfusion independent (no platelet transfusions within 1 week of the start date of protocol therapy).

Patients with bone marrow involvement on the phase 2 portion of the study must meet the following hematologic criteria. These patients will not be evaluable for hematologic toxicity or hematologic DLT:

- a. ANC $\geq 750/\mu\text{L}$ (no hematopoietic growth factors within 7 days of the start date of protocol therapy); and
- b. Platelet count $\geq 50,000/\mu\text{L}$ (platelet transfusions allowed).

3.2.10.2 Renal Function:

Patients must have adequate renal function defined as age-adjusted serum creatinine $\leq 1.5 \times$ normal for age (see below):

Age	Maximum Allowable Serum Creatinine
≤ 5 years	0.8 mg/dL
> 5 and ≤ 10 years	1.0 mg/dL
> 10 and ≤ 15 years	1.2 mg/dL
> 15 years	1.5 mg/dL

3.2.10.3 Liver Function:

- a. Total bilirubin $\leq 1.5 \times$ normal for age;
- b. SGPT (ALT) ≤ 135 U/L ($\leq 3 \times$ ULN) for the oral solution cohort and ≤ 225 ($\leq 5 \times$ ULN) for the phase 2 portion of the study. Note that for ALT, the upper limit of normal for all sites is defined as 45 U/L.

3.2.10.4 Reproductive Function:

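### The entry blood count can be 21 days old at therapy start, but the support-free week is counted back only from therapy start, so a supported count can qualify a patient

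*Combined protocol and SAP*

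**What the plan says.** Three timing rules meet here.

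- **Age of the count.** Section 7.1: "All blood and urine studies must be performed within 2 weeks prior to study enrollment".
- **Enrollment to start.** Section 3.1: "Patients are required to start protocol therapy within 1 week of study enrollment". Section 7.1 repeats the rule. Section 3.1 also fixes the anchor: "The start of protocol therapy is defined as the start of oral cephalosporin in Day -1".
- **Support-free period.** Section 3.2.10.1 attaches to the ANC limit "no hematopoietic growth factors within 7 days of the start date of protocol therapy", and to the platelet limit "no platelet transfusions within 1 week of the start date of protocol therapy". Section 3.2.8 counts its own 7-day growth factor rule from the same anchor.

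Section 3.1 adds: "The eligibility criteria listed below are interpreted literally and cannot be waived".

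The entry counts matter after entry too. Under section 3.2.10.1, an oral solution patient with marrow disease who meets them is evaluable for hematologic toxicity. Section 10.4 describes the phase 2 patients inevaluable for hematologic DLT as those with marrow involvement and low baseline counts. Section 4.1 uses the entry counts to set what a patient must recover to before the next cycle, and section 4.4 defines hematologic DLT as failure to reach those values by day 36.

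**The concern.** The limits of 1,000 for ANC and 100,000 for platelets are evidently meant to describe unsupported marrow function. The rule that should secure this looks at the wrong week: it governs support just before therapy, while the count may come from an earlier week in which support was still being given.

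Section 2.13 names hematologic toxicity as the primary DLT, and the current definition rests wholly on count recovery. A patient whose unsupported platelets are low at entry could fail recovery because of marrow reserve, and the failure could be attributed to the dose. Few events decide the matter. In the oral solution cohort, two DLTs in up to six patients exceed the MTD (section 10.3). In phase 2, two in the first six trigger a formal review (section 10.4). One misattributed event is half of either total.

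**Working it through.** The plan states no maximum age for the count at therapy start, so there is no figure of its own to reproduce. The check is date arithmetic, followed by a search for a later safeguard.

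**Inputs.** Count window: 14 days back from enrollment (section 7.1). Gap from enrollment to start: g = 0 to 7 days (sections 3.1 and 7.1). Support-free period: 7 days back from start (sections 3.2.8 and 3.2.10.1). Therapy start: Day -1, which section 4.2.5 places 2 days before irinotecan.

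**Age of the count.** The oldest permitted count is 14 + g days before start.
- g = 0: 14 days.
- g = 7: 14 + 7 = 21 days, or 21 + 2 = 23 days before the first irinotecan dose.

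**Exposed window.** A count taken 8 or more days before start lies outside the support-free week. The exposed days run from 8 to 14 + g, which is (14 + g) - 7 = 7 + g days.
- g = 0: 7 days (days 8 to 14 before start).
- g = 7: 14 days (days 8 to 21 before start).

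**Worked case.** Count 15 days before start, on filgrastim or one day after a platelet transfusion; last support 8 days before start; enrollment 7 days before start. Count to enrollment is 15 - 7 = 8 days, within 14. Enrollment to start is 7 days, within 7. Last support is 8 days before start, outside the barred week. Every dated rule is met.

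**Is there a later check?**
- Section 4.1 repeats the organ function requirements before each cycle but excepts ANC and platelets. Its replacement values govern only the next cycle.
- Footnote 8 to the section 7.1 table says "All observations timed for the start of a cycle are to be obtained prior to the start of Day 1 therapy", but it is attached only to the Cycles 2-34 column.
- Cycle 1 has twice-weekly blood counts, but nothing links them to eligibility or evaluability.

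**Which count matters more?**

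| | Entry limit | Recovery, standard class | Recovery, phase 2 marrow disease with low entry counts |
|---|---|---|---|
| Platelets | 100,000 | 75,000, untransfused | 50,000, transfusions allowed |
| ANC | 1,000 | 750, more than 24 hours off growth factor | 750, same condition |

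For platelets, the class set at entry changes both the threshold and whether transfusion is allowed. For ANC the two classes are the same. Section 4.2.4 requires growth factor from day 8 and recommends filgrastim until ANC exceeds 2,000 after the nadir. A patient who reached 1,000 on support at entry is therefore judged at 750 with support only recently stopped. That makes platelets the main practical route.

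**The case against.** The strongest case is that the gap exists on paper but does little.

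- **Transfusion independence.** A count just after a transfusion is not transfusion independent in ordinary language, and a truly dependent patient would probably need platelets again in the barred week. This narrows the platelet route. It does not close it, because the only explanation given for the term is the clause tied to therapy start.
- **Other safeguards.** Section 3.2.8 requires full recovery from acute effects of prior treatment, and that is to be read literally too. Section 3.1 has eligibility verified centrally. Neither rule dates the count against support, and the eligibility worksheet is not in the documents, so its content is unknown.
- **Not every low count leads to a DLT.** Recovery limits are below entry limits. A patient with unsupported platelets between 75,000 and 100,000 already meets the recovery value at baseline; only one below 75,000 starts under it. This stands.
- **Phase 2 consequences.** Crossing a boundary prompts a review at which baseline counts can be weighed, and the error is toward caution. This also stands.

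A reader might infer a measurable distortion of the MTD decision, taking the 1/6 DLT rate at dose level 2B as a base and giving one patient in six a raised risk. The documents do not support that. Section 2.12 reports the single 2B event as prolonged grade 4 neutropenia, and Amendment 6 removed grade 4 neutropenia lasting more than a week from the DLT definition (section 2.13). The oral solution cohort starts at 1B, where tablets gave 0/6. Any raised risk, and any share of patients entering this way, would be invented.

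**Conclusion.** The anchor dates do not match, and read literally they let a growth-factor-supported or transfused count qualify a patient and set evaluability and recovery class. The count can be 21 days old at therapy start, and the exposed window is 7 to 14 days wide depending on the gap from enrollment to start. This follows from the stated intervals alone.

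The effect on DLT counts rests on an assumption that the documents cannot test: that some patients enter with support given around the count and none in the final week. The frequency is unknown and may be small. The concern is mainly platelets; a claim that both recovery thresholds become stricter would be wrong, since the ANC value is 750 in either class. This is a gap in an eligibility rule worth closing because closing it is cheap, not a demonstrated bias in the dose decision.

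**What to change.** In section 3.2.10.1, with a cross-reference in section 7.1, reconcile the two anchors: apply the existing 7-day transfusion-free and growth-factor-free interval to the date of the blood count used for eligibility as well as to the start of protocol therapy, wherever that interval already applies. The number of days with a qualifying supported count then falls to zero. No count limit, dose or sample size changes.

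The cost is an occasional repeat blood count or a short enrollment delay. The change does not shorten the permitted 21 days; it only ensures that the count was unsupported when taken.

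Extending footnote 8 to cycle 1 is not a substitute. It refers to criteria for a subsequent cycle and supplies no cycle 1 threshold. Using a new pre-treatment count to reclassify patients would also need an inevaluable class that exists only for phase 2 patients with marrow involvement (sections 3.2.10.1 and 10.4), leaving other enrolled patients with no defined status.
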